**Youth FORWARD scale-up study AIM 3:**

**AIM 3 (Clinical Effectiveness):** To compare clinical effectiveness of YRI when delivered via the EPP platform to results of our previous randomized control trial (RCT) of YRI as measured by improved mental health and reduced functional impairments among high-risk youth. Emotion regulation will be examined as a major mechanism by which the YRI improves behavior of treated youth and their functioning in the ENTR.

*Hypothesis 3(a): Participants who are exposed to YRI will demonstrate greater reduction in mental health and functional problems than participants who do not receive the YRI intervention; emotion regulation (as measured using the Disturbances in Emotion Regulation Scale) will operate as a major mechanism of YRI improvements; high comorbidity will be a treatment modifier.*

*Hypothesis 3(b): Improvements in mental health and functioning due to YRI will lead to (mediate) greater employment outcomes and superior economic self-sufficiency over time.*

*Hypothesis 3(c): Homelessness, orphanhood, young parenthood, and high problems in emotion regulation comorbid with other mental health conditions will be moderators lessening the effectiveness of YRI.*

The table below outlines study primary outcomes, primary predictors, moderators and hypothesized mediators.

Primary Outcome Variables
Difficulties in Emotion Regulation (DERS)
Hopkins Symptom Checklist (HSCL)
Oxford Measure of Psychosocial Adjustment (OMPA)
Employment
Economic Self-Sufficiency
Primary Predictor Variables
Time
Group Membership (ENTR-only, YRI+ENTR, Control)
Possible Moderators
Gender
Age

Education Level
Literacy
Session Attendance
Hypothesized Mediators
Emotion regulation (DERS)
Oxford Measure of Psychosocial Adjustment (OMPA)
Hopkins Symptom Checklist (HSCL)
WHO Disability Assessment Scheduled (WHODAS)

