## **Part II Emotion Regulation as the Mechanism Through which the YRI improvements operate**

**Primary Outcomes:** OMPA internalizing, OMPA externalizing

**Primary Predictor:** Group Membership (Control, ENTR-only, YRI+ENTR)

**Hypothesized Mediator:** Emotion Regulation (assessed by DERS)

**Possible Moderators:** Subject gender, age, education level/literacy, session attendance

We hypothesize that the YRI improvements may operate through changes in emotion regulation. This is a proposed mediation model where the primary predictor is group membership, the primary outcome is mental health at 12 months, and the mediator is emotion regulation as measured by the Difficulties in Emotion Regulation (DERS) at six weeks. We will test for the indirect effect of group membership on Mental Health Status using conditional process analysis (Hayes, 2013). The conditional process equations are (if gender modifies the indirect effect for example):

$$DERS(6\ weeks) = B_0 + a * X$$

$$MH(12\ months) = B_0 + cX + b_1 * DERS(6\ weeks) + b_2 * G + b_3 * G * DERS.$$

Where  $X$  is group membership and  $G$  is gender. The coefficient  $a$  quantifies the effect of group membership on emotion regulation and  $b$  quantifies the effect emotion regulation on mental health independent of group membership. The product  $p = a(b_1 + b_3 * G)$  is the *indirect effect* of group membership on Mental Health. We can test for the significance (null hypothesis  $p = 0$ ) via

bootstrapping. A significant (at 0.05) is indication that emotion regulation mediates the relationship between the YRI effects and mental health. For outcomes that are binary we will need to use the KHB method (Breen, Karlson, & Holm, 2013) to rescale the regression coefficients correctly. A strength of this analysis is that group membership, emotion dysregulation and Mental Health are measured at three different time points which is necessary for causal mediation (though not sufficient).

As an alternative we can test for mediation using Structural Equation Modeling (SEM). This approach is more flexible than conditional process analysis and may allow us to use full-information maximum likelihood (FIML) as opposed to multiple imputation. All causal models will be evaluated for the possible effects of unmeasured confounders (VanderWeele & Ding, 2017).

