### **Data Analysis Plan for Hypothesis 3b:**

*Hypothesis 3(b): Improvements in mental health and functioning due to YRI will lead to (mediate) greater employment outcomes and superior economic self-sufficiency over time.*

**Primary Outcome:** Measures of employment and superior economic sufficiency.

**Primary Predictor:** Group membership.

**Mediator:** Mental Health as measured by the HSCL, OMPA; functioning as measured by WHODAS

**Possible Moderators:** Subject gender, age, education level/literacy, session attendance

Similar to Aim 3(a) we will test for mediation using condition process analysis the process equations are similar:

$$MH(12\ months) = B_0 + a * X$$

$$Employment = B_0 + B_0 + cX + b_1 * MH + b_2 * G + b_3 * G * MH$$

The indirect effect of mental health on employment and economic self-sufficiency is quantified by the product  $p = a(b_1 + b_3 * G)$ . We will use a bootstrap test to access significance. Binary outcomes will need to be adjusted using KMB method. The size and direction of effects will be determined by the estimates of the regression coefficients.

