### **Data Analysis Plan for Hypothesis 3c:**

*Hypothesis 3(c): Homelessness, orphanhood, young parenthood, and high problems in emotion regulation comorbid with other mental health conditions will be moderators lessening the effectiveness of YRI.*

**Primary Outcome:** Measures of employment and superior economic sufficiency

**Primary Predictor:** Group Membership

**Mediator:** Mental Health

**Possible Moderators:** Subject gender, age, education level/literacy, session attendance, emotion regulation.

To the mediation model described in hypothesis 3b we will add terms to account for the moderating influences of gender, age, education level/literacy, session attendance, and emotion regulation. For purposes of exposition we will generically label the moderator as  $W$ . Our hypothesis is that moderators act on the influence of group membership and mental health. The conditional process equations in this case are (only one moderator was included for brevity):

$$MH(12\ months) = B_0 + a * X$$

$$Employment = B_0 + B_0 + cX + b_1 * MH + b_2 * G + b_3 * G * MH$$

In these equations the indirect effect of group membership on employment and economic self-sufficiency is  $(a_1 + a_3 * W) * b$ . The value  $a_3 * W * b$  is sometimes called the index of moderated mediation. In the case of dichotomous  $W$  (gender, homelessness, young parenthood) this value reduces to  $a_3 * b$  and is interpreted as the difference of the indirect effect of group membership on employment and economic self-sufficiency of the two  $W$  groups. Test for moderation can be directly from the coefficient  $a_3$ . Alternative tactics include SEM as opposed to conditional process equations. KHB rescaling will be needed since moderators, mediators, and outcomes represent different variable types (binary, continuous etc.). In practice we can include all moderators in the model simultaneously.

We can also verify which path the candidate variables modify (we assumed the path from primary predictor to mediator). This can be done in the context of SEM models. We can fit models where the moderators act on the paths from mediator to outcome or both. Using fit indices such RMSEA we can compare model fits to determine which model best matches the data.

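### The printed H3b employment equation leaves out six-week DERS, so the mental-health-to-employment path is open to confounding by a measured mechanism that the plan itself proposes

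*Combined protocol and SAP*

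**What the plan says.** Three parts of the combined protocol and SAP bear on this.

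- **AIM 3 section:** "Emotion regulation will be examined as a major mechanism by which the YRI improves behavior of treated youth and their functioning in the ENTR". DERS is listed first among the hypothesised mediators, and Hypothesis 3(b) has mental health and functioning together leading to employment.
- **Part II of the Hypothesis 3a plan:** "We hypothesize that the YRI improvements may operate through changes in emotion regulation". In that model "the mediator is emotion regulation as measured by the Difficulties in Emotion Regulation (DERS) at six weeks", the outcome is mental health at 12 months, and the coefficient a "quantifies the effect of group membership on emotion regulation". Six-week DERS is thus affected by group and comes before mental health.
- **Data Analysis Plan for Hypothesis 3b:** "Similar to Aim 3(a) we will test for mediation using condition process analysis the process equations are similar". The mediators are given as "Mental Health as measured by the HSCL, OMPA; functioning as measured by WHODAS"; DERS is not named. The outcome model is "Employment = B_0 + B_0 + cX + b_1 * MH + b_2 * G + b_3 * G * MH".

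The 3c plan prints the same outcome equation. It does list emotion regulation, but only among its possible moderators: "Subject gender, age, education level/literacy, session attendance, emotion regulation". No measurement time is given for it there, and the text takes the group-to-mediator path as the default place for moderators to act.

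**The concern.** Randomisation protects the effect of group on mental health. It does not protect the effect of mental health on employment, which is estimated from observed variation in mental health within arms. Any common cause of mental health and employment that is left out biases that second path.

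On the plan's own theory six-week DERS is a candidate for such a cause. It arises after randomisation and the YRI is meant to change it, so baseline covariates cannot fully stand in for it. If it is left out, b_1 absorbs whatever DERS does to employment outside the fitted mediator. The product of paths then reports that as mediation by mental health. H3b could be declared confirmed when better emotion regulation, and not better mental health, produced the economic gain. The plan treats these as separate mechanisms, so the distinction matters for what the trial concludes.

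**Working it through.** The plan gives no effect size, standard deviation or sample size for its mediation models, so there is no figure to reproduce. The documents supply the structure; every number below is an assumption.

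**Structure.** Group (X) affects six-week DERS (L), and L affects 12-month mental health (M): Part II. L affects functioning in the ENTR: AIM 3 section. Functioning leads to employment (Y): Hypothesis 3(b). The path from L to Y outside M is inferred from the last two.

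**Formula.** Scale L and M to within-arm SD 1, with higher scores worse:

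- L = a_L X + error
- M = g X + ρ L + error
- Y = c X + b M + θ L + error

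Here ρ is the within-arm DERS–mental health correlation, and θ is the DERS effect on employment that does not pass through M. Regressing Y on X and M alone gives E[b_1] = b + θρ. The total group effect on M is a = g + ρ a_L, so the bias in the indirect effect is a × θ × ρ.

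**No true mental-health effect (b = 0).** Assumptions: a_L = −0.3, g = −0.1, c = 0; two arms, no clustering, no FDR adjustment. The simulation used 1,000 runs, with a 95% Monte Carlo interval for the product in place of the bootstrap.

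| ρ | θ | Bias in b_1 = θρ | False mediation without DERS, 200 / 400 per arm | With DERS added, 200 / 400 per arm |
|---|---|---|---|---|
| 0.5 | 0 | 0 | 3% / 5% | 4% / 4% |
| 0.2 | −0.1 | −0.02 | 2% / 5% | 2% / 2% |
| 0.35 | −0.2 | −0.07 | 11% / 38% | 2% / 3% |
| 0.5 | −0.3 | −0.15 | 54% / 91% | 3% / 4% |

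**A true effect (b = −0.20, ρ = 0.35, θ = −0.2, 400 per arm).** a = −0.1 + 0.35 × (−0.3) = −0.205.

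- True indirect effect: −0.205 × −0.20 = 0.041.
- Without DERS: b_1 = −0.20 − 0.07 = −0.27, and the indirect effect is −0.205 × −0.27 = 0.055. Since 0.27 / 0.20 = 1.35, it is about 35% too large.
- With DERS in the employment equation, the simulated b_1 is −0.200 and the indirect effect 0.041. The test rejects in 81% of runs either way.

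**A second set of inputs.** Here DERS affects mental health by 0.5 and the outcome by −0.3 SD per SD, and group acts on mental health only through DERS. With 300 per arm, false mediation is 41% without DERS and 2% with it when the YRI moves DERS by 0.3 SD; it is 81% and 5% at 0.5 SD. Over 150–500 per arm the ranges are 16–98% and 1–6%. Reducing the direct effect to −0.1 and the correlation to 0.3 gives 1–12% without DERS; removing the direct effect gives 0–4%.

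**Where WHODAS sits.** If DERS reaches the outcome only through functioning, and functioning is fitted beside mental health, false mental-health mediation is 2–4% even without DERS. If mental health is fitted alone, it is 33–96%.

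**The case against.** **The path from DERS to employment is not stated.** The AIM 3 text speaks of behaviour and functioning in the ENTR, not of employment. A reader might infer that the plan asserts a direct DERS effect on employment and that H3b is therefore certainly confounded. The documents do not support that: the link is an inference, though a natural one, because H3b has functioning leading to employment. WHODAS is also a named H3b mediator. Fitted jointly with mental health, it could block part or all of the route. This stands, but the printed equation has one mediator term and the plan does not say whether the mediators enter together.

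**The equations are schematic.** The cluster-level baseline outcome is promised for all analyses and appears in none of the process equations, so a missing term is weak evidence of what will be fitted. That is fair. Even so, nothing elsewhere commits the plan to DERS in the 3b model. The general statement on individual-level confounders sits under 3a and does not name it. The promised sensitivity analysis is for unmeasured confounders, whereas DERS is measured. The SEM alternative is optional and has no specified path from DERS to employment.

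**H3c is different.** A reader might take the omission to apply equally there. It does not: emotion regulation is a listed moderator, and the printed equation places its example moderator in the outcome model with a main effect. What remains open in 3c is the time point and the equation in which the term sits.

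**The large error rates depend on strong inputs.** A reader might take 16–98% as the expected error rate. That range holds the DERS effects at 0.5 and −0.3 and leaves out the end at which there is no bias.

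**Adding DERS does not make b_1 causal.** With a shared unmeasured cause of 0.3 SD, false mediation was still 18–82% with DERS included. This also stands.

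**Conclusion.** The concern holds for H3b in conditional form. As printed, the employment equation leaves out a measured, YRI-affected variable that the plan's own theory places before mental health and connects to functioning. If that variable affects employment by any route outside the fitted mediator, b_1 is biased by about θρ and the indirect effect is misattributed to mental health.

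The size cannot be found from the documents. Under the assumed inputs, false mediation is about 0–5% when the direct path is absent or both links are at their weakest, and passes 90% when both are strong and the arms are large. These figures assume linear models, two arms and no clustering.

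The documents do not show that bias is present, that H3c shares the problem to the same degree, or that a single extra term settles the matter under the planned interaction and binary outcomes. The change should be made before analysis. Confidence is moderate, because the path from DERS to employment is inferred.

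**What to change.** 1. Add six-week DERS as a main effect to the H3b employment and self-sufficiency equation. State which scheduled visit this is. It is presumably Post-YRI, but neither list of assessment times in the 3a plan names six weeks, so availability of the measurement should be confirmed.
2. Leave the group-to-mental-health equation without DERS, so that a remains the total group effect. In a linear model without interactions, the product is then the whole effect carried through mental health, including the part that began with DERS.
3. Fit WHODAS jointly with mental health, or state that it is fitted separately.
4. Report the DERS-adjusted result beside the unadjusted one.
5. For the gender-by-mental-health term and for binary outcomes, state the estimand: for example an interventional or path-specific indirect effect, or a sequential-mediator SEM with a direct path from DERS to employment.
6. In H3c, only ensure that the six-week main effect of emotion regulation is in the employment equation.

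The cost is SAP wording, a little more analysis work, and a slightly wider interval for b_1 because DERS and mental health are correlated. The change gives no protection against unmeasured causes shared by mental health and employment, so the planned sensitivity analysis is still needed.

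### Hypotheses 3b and 3c take mental health at 12 months, the last listed wave, as mediator of undated employment, so employment improving mental health could be reported as mediation

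*Combined protocol and SAP*

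**What the plan says.** Hypothesis 3b holds that mental-health and functional gains from the YRI bring about "greater employment outcomes and superior economic self-sufficiency over time". The Data Analysis Plan for Hypothesis 3b introduces the model with "Similar to Aim 3(a) we will test for mediation using condition process analysis the process equations are similar" and then prints two equations:

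- Mediator: "MH(12\ months) = B_0 + a * X"
- Outcome: "Employment = B_0 + B_0 + cX + b_1 * MH + b_2 * G + b_3 * G * MH"

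The mediator is dated and the outcome is not. The Data Analysis Plan for Hypothesis 3c prints the same pair.

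The model being imitated is in Part II of Hypothesis 3a. There the mediator is "Difficulties in Emotion Regulation (DERS) at six weeks" and "the primary outcome is mental health at 12 months". The plan counts this spacing as a strength: group, mediator and outcome are "measured at three different time points which is necessary for causal mediation (though not sufficient".

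**The concern.** Mediation through mental health is a claim about direction: the intervention changes mental health, and that change then alters employment. If both are read at the same visit, or employment is read first, the regression of employment on mental health also picks up any effect of employment on mental health. Such an effect is plausible here, because two of the three arms receive entrepreneurship training, which may act on work directly.

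The Aim 3 table lists employment and economic self-sufficiency among the primary outcome variables, and the sections for 3b and 3c are the only analysis sections that name them as outcomes. What is at stake is whether the trial may say that mental-health gains led to employment.

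**Working it through.** **Time indices side by side**

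| Analysis | Mediator | Outcome | Mediator first? |
|---|---|---|---|
| 3a, Part II | DERS, six weeks | Mental health, 12 months | Yes |
| 3b | Mental health, 12 months | Employment, undated | Not on the listed waves |
| 3c | Mental health, 12 months | Employment, undated | Not on the listed waves |

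The Hypothesis 3a section gives two wave lists. One has four waves (baseline, post-YRI, post-ENTR, 12 months) and the other three (baseline, post-training, 12 months). They differ, but both end at 12 months, and no later assessment appears anywhere.

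**Planned safeguards.** None restores time order. Part II says "All causal models will be evaluated for the possible effects of unmeasured confounders", which concerns confounding, not direction. The SEM comparisons under 3c vary which path is moderated, not the direction between mental health and employment. Cluster-level baseline control, individual-level confounders and the FDR adjustment do not create time order either.

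**Size of the false indirect effect.** The plan gives no sample size, power or effect size for 3b or 3c, so there is no figure to reproduce and every input below is assumed: two arms (X = 0 or 1), N = 500, no clustering, no FDR, gender term dropped, unit error variances. The data are purely reverse-causal:

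- E = 0.2X + e
- M = m·X + d·E + e, where m is the arm's direct effect on mental health

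Fitting the plan's equations gives a = m + 0.2d and b = d/(1 + d²). The true indirect effect is 0. With m = 0.3, the product ab is:

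- d = 0.1: 0.32 × 0.1/1.01 = 0.032
- d = 0.2: 0.34 × 0.2/1.04 = 0.065
- d = 0.3: 0.36 × 0.3/1.09 = 0.099

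If instead mental health truly raises same-wave employment by d, the indirect effect is 0.3d = 0.030, 0.060 and 0.090. The two directions give nearly the same estimate.

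**How often mediation is declared** (2,000 simulated trials per scenario; 95% Monte Carlo interval for ab in place of the bootstrap)

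| Scenario | d = 0.1 | 0.2 | 0.3 |
|---|---|---|---|
| Reverse only, m = 0.3 | 55% | 95% | 97% |
| Reverse only, m = 0.15 | 24% | 53% | 61% |
| Reverse only, m = 0 | 3% | 7% | 9% |
| Reverse only, m = 0.3, N = 250 | 22% | 64% | 78% |
| True mediation, arm effect on M 0.3 | 53% | 91% | 93% |

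At d = 0 and m = 0.3 the rate is 5%, as it should be. Binary employment with a logistic model gives 55/95/97%, 24/54/61% and 3/7/11% for the three values of m at N = 500.

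The low rates at m = 0 also depend on the assumed 0.2 SD and d. With m = 0, an arm effect on employment of 0.3 or 0.5 and a reverse effect of 0.3 or 0.5, a percentile bootstrap declared mediation in 14–36% of trials at 100 per arm, 15–62% at 200 and 20–86% at 400.

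**What an earlier mediator achieves.** Three waves, reverse causation only, employment persistence ρ from 0.3 to 0.7, and E0 and M0 standard normal:

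- E1 = ρE0 + 0.2X + e
- M1 = 0.5M0 + 0.3X + dE1 + e
- E2 = ρE1 + 0.2(1 − ρ)X + e
- M2 = 0.5M1 + 0.15X + dE2 + e

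As written, the fit is M2 on X, then E2 on X and M2. The alternative fits M1 on X, M0 and E0, then E2 on X, M0, E0 and M1. With unit errors its false indirect effect is (0.3 + 0.2d)·ρd/(1 + d²); at ρ = 0.5 and d = 0.2 this is 0.34 × 0.1/1.04 = 0.033, which the simulation reproduces. Scaled errors use variances 1 − ρ² for E and 0.75 for M.

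- At d = 0.2, false mediation falls from 92–94% to 23–66% (unit errors) or from 97–98% to 28–54% (scaled errors).
- With the earlier mediator it is 9–21% (unit) or 11–18% (scaled) at d = 0.1, and 42–92% or 52–87% at d = 0.3.
- The mean false indirect effect falls by 58–71% over all d. In the worst case (d = 0.3, ρ = 0.7, unit errors) the rate stays at about 93% even though the mean effect falls by about 58%.

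**The case against.** The strongest reply is that this argues from silence. Employment is undated, both wave lists sit under Hypothesis 3a, whose outcomes do not include employment, and the hypothesis speaks of change over time. A later employment assessment outside this document cannot be excluded. That stands, and it is why the point is limited to the listed waves.

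Second, the 12-month index may be a slip. The equations are templates: the intercept is printed twice, and the 3c equations lack the moderator terms that the surrounding text relies on. Mental health at 12 months was the outcome in Part II and may simply have been carried over. This is plausible, but the index appears in both sections, and an analyst who follows it uses a mediator from the last wave.

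Third, the percentages rest on assumed inputs, and the high rates in the main illustration need a direct arm effect on mental health. That also stands. The finding rests on the time indices; the rates only show that the consequence need not be small.

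Fourth, the remedy is partial and asks for more than dates. This is true: an earlier mediator can leave substantial false mediation, and the documents do not confirm that all the needed variables are collected.

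**Conclusion.** The concern holds. On the listed waves, 3b and 3c do not meet the plan's own necessary condition for causal mediation, and the printed model cannot tell mental health improving employment from the reverse. This rests on one inference, that employment is not assessed after 12 months.

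The simulated rates, from 3% to 97% at N = 500, describe assumed scenarios and are not this trial's error rate. Only the mediation claims in 3b and 3c are affected. This should be fixed before the mediation results are interpreted.

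**What to change.** In the sections for 3b and 3c:

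1. Date employment and economic self-sufficiency at 12 months.
2. Take HSCL, OMPA and WHODAS from one named post-baseline wave before 12 months, after reconciling the two wave lists with the six-week assessment in Part II.
3. Adjust both equations for each youth's baseline mental health and, where collected, baseline employment.
4. As a sensitivity analysis only, and where collected, add employment at the mediator's wave and report results with and without it.
5. Keep the unmeasured-confounder check, and state that an earlier wave reduces but does not eliminate reverse causation.

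If the 12-month mediator is kept, report an association and do not claim that mental-health gains led to employment.

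**Cost.** This is SAP wording, with no new visit for the scales already listed with earlier waves: HSCL, OMPA Externalizing and WHODAS. Three points need confirming: whether the rest of the OMPA is available at those waves, whether employment is collected at the mediator's wave, and whether the work and income items used for cluster matching correspond to the employment outcome. The earlier mediator's indirect effect may be smaller and less precise.

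Item 4 should not be the main model. Adding the term brings false mediation down to 4.0–5.4%, but it can erase real mediation. When mental health truly raises same-wave employment that persists (ρ = 0.5, unit errors, effect 0.1, 0.2 and 0.3), detection is 14%, 44% and 77% without the term and 3–6% with it.
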